# 9.5.2 Safety analyses

Safety and tolerability data will be presented by treatment group using the safety population.

Data from all cycles of treatment will be combined in the presentation of safety data. AEs (both in terms of Medical Dictionary for Regulatory Activities preferred terms and CTCAE grade) will be listed individually by patient. The number of patients experiencing each AE will be summarized by treatment group and CTCAE grade. Additionally, data presentations of the rate of AEs per person-years at risk may be produced.

Other safety data will be assessed in terms of clinical laboratory findings (including chemistry, hematology, and urinalysis), physical examinations, vital signs, and ECGs. Exposure to durvalumab monotherapy, durvalumab and tremelimumab combination therapy, and placebo will be summarized. Time on study; durvalumab monotherapy, durvalumab and tremelimumab combination therapy, and placebo dose delays will also be summarized. At the end of the study, appropriate summaries of all safety data will be produced, as defined in the SAP.

A listing of all subjects affected by the COVID-19 pandemic, and subjects with reported issues in the Clinical Trial Management System due to COVID-19 pandemic will be generated. In addition, all COVID-19 related non-important PDs and issues will be summarized and listed. Additional analyses might be conducted to investigate the impact of COVID-19 on study endpoints.

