- Placebo: Placebo saline solution (IV) q4w in combination with a second placebo saline solution (IV) q4w for up to 4 doses/cycles each, followed by a single placebo saline solution q4w. The first placebo saline solution monotherapy dose q4w will be 4 weeks after the final dose of the 2 placebo saline solutions in combination.

Treatment in all treatment groups will be administered beginning on Day 1 until clinical/RECIST 1.1-defined radiological progression, until intolerable toxicity, or for a maximum of 24 months, whichever occurs first.

Patients who have discontinued treatment due to toxicity, symptomatic deterioration, or clinical progression will be followed up with tumor assessments until RECIST 1.1-defined radiological progression plus one follow-up scan or until death (whichever comes first) and followed for survival.

This main body of this Statistical Analysis Plan (SAP) outlines the pre-specified analyses for the overall study population (global cohort). Appendix D outlines pre-specified analyses that may be conducted for the China sub-population (China cohort) and Asia subset (patients enrolled from Asian countries) of study D933QC00001 to support ADRIATIC submission in China, which will be reported outside of the CSR.

Data Monitoring Committee:

An Independent Data Monitoring Committee (IDMC) comprised of independent experts will be convened to review planned unblinded safety data. This planned safety review will take place after the first 20 patients have been randomized into each of the 3 treatment groups (i.e. after a total of 60 patients have been randomized to the study). In addition, the IDMC will review planned interim analyses on overall efficacy and safety and inform the sponsor whether the interim boundaries are met.

Details on the IDMC are provided in Section 5.2. Full details of the IDMC procedures, processes, and interim analyses can be found in the IDMC Charter.

The general study design is summarized in Figure 1.

[figure not shown]

Figure 1 Study design

BID Twice daily; CR Complete response; CRT Concurrent Chemoradiation therapy; EP Etoposide and cisplatin chemotherapy; LS-SCLC Limited stage small-cell lung cancer; PCI Prophylactic cranial irradiation; PD Progressive disease; PR Partial response; PS Performance status; QD Once daily; R Randomization; RT Radiotherapy; SD Stable disease.

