1.3 Number of Subjects

The study will plan to enroll approximately 965 patients globally in order to randomize approximately 724 patients to 1 of 3 treatment groups: durvalumab monotherapy (approximately 262 patients), placebo (approximately 262 patients), or durvalumab + tremelimumab combination therapy (approximately 200 patients) over a period of approximately 38 months. Initially, patients will be randomized 1:1:1 to the 3 treatment groups. Following implementation of CSP Version 4, once 600 patients have been randomized, a further 124 patients will subsequently be randomized 1:1 to durvalumab monotherapy or placebo until a total of approximately 724 patients have been randomized.

The study has dual primary objectives which are to assess the efficacy of durvalumab monotherapy compared to placebo in terms of PFS per RECIST 1.1 as assessed by BICR, and OS.

The primary PFS analysis will occur at the earliest of:

- 1. When approximately 370 PFS BICR events have occurred (70.6% maturity) in the durvalumab monotherapy and placebo treatment groups
- 2. At OS-IA2, if OS-IA2 is statistically significant (durvalumab monotherapy vs placebo)
- 3. Approximately 36 months after the last patient randomized

If the true PFS HR is 0.65 for durvalumab monotherapy versus placebo, with 370 PFS BICR events, the study will have approximately 90% power to demonstrate a statistically significant difference in PFS between durvalumab monotherapy and placebo, with an overall 2-sided significance level of 0.5%. The true HR of 0.65 translates to a 5.4 month benefit in median PFS over 10 months on placebo if PFS is exponentially distributed. The smallest treatment difference that would be statistically significant is a HR of 0.743 (Critical value (CV)). At this time, approximately 309 PFS BICR events are also expected to have occurred in the durvalumab in combination with tremelimumab and placebo treatment groups. A recruitment period of approximately 38 months was assumed in the CSP for the primary PFS analysis.

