3.4.5 Treatment exposure

Exposure will be defined as follows and calculated separately for "durvalumab or placebo" and "tremelimumab or placebo". Exposure in each treatment group is the maximum of calculated values from the two components.

Total (or intended) exposure

• Total (or intended) exposure = the earliest of (date of last dose date of study drug where valid dose is considered + 27 days, death date or DCO) – first dose date + 1 day.

Actual exposure

 Actual exposure is defined as intended exposure, but excluding total duration of dose interruptions and cycle delays

Dose reductions for durvalumab, tremelimumab, or placebo are not permitted per the CSP. The actual exposure calculation makes no adjustment for any dose reductions that may have occurred.

Exposure will also be measured by the number of cycles received. If a cycle is prolonged due to toxicity, this should still be counted as one cycle. A cycle will be counted if treatment is started even if the full dose is not delivered.

Calculation of duration of dose delays (for actual exposure):

• Duration of dose delays will be calculated as follows for each dose and summed over the entire dosing period to obtain a total duration of dose delay:

If Date of the dose – Date of the previous dose \geq 31 days (28 + 3 days) then

Duration of dose delay= Date of the dose - Date of previous dose - 31 days

Otherwise duration of dose delay will be zero.

Valid dose rule

A valid dose of treatment will be classed as:

- At least one record with "DURVALUMAB/PLACEBO" or "TREMELIMUMAB/PLACEBO" and where the start date is non-missing.
- Volume of infusion must be greater than 0 (before after)
- Study Drug Dose per administration must not be 0 or missing.

Dose unit conversion

Dose of durvalumab and tremelimumab is collected in mL. To be reported in units of mg using the following conversions:

Durvalumab:

$$dose in mg = dose in mL x 50$$

e.g.
$$30mL \times 50 = 1500mg$$

Tremelimumab:

$$dose in mg = dose in mL x 19.73684211$$

e.g.
$$3.8$$
mL \times $19.73684211 = 75$ mg

Patients who permanently discontinue during a dose delay

If a decision is made to permanently discontinue study treatment in-between cycles or during a dose delay, then the date of last administration of study medication recorded will be used in the programming.

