4.2.13.1 Adverse events

All AEs, both in terms of current MedDRA preferred term and CTCAE grade, will be summarized descriptively by count (n) and percentage (%) for each treatment group. The current MedDRA dictionary at the time of database lock will be used for coding wherever possible. The majority of the AE summaries, unless stated otherwise, will be based on TEAEs. Any AE occurring before study treatment (i.e. before the administration of the first dose on Study Day 1) will be included in the AE listings, but will not be included in the summary tables (unless otherwise stated). These will be referred to as 'pre-treatment'. However, any AE occurring before the administration of the first dose on Study Day 1 that is ongoing and increases in severity after the first dose will be regarded as treatment emergent and thus will be included in the majority of summary tables.

AEs observed up until 90 days following discontinuation of the study treatment or until the initiation of the first subsequent anti-cancer therapy following discontinuation of study treatment (whichever occurs first) will be used for reporting of all the AE summary tables. This will more accurately depict AEs attributable to study treatment only as some of AEs up

to 90 days following discontinuation of the study treatment are likely to be attributable to subsequent therapy.

However, to assess the longer-term toxicity profile, some of the AE summaries may also be produced containing AEs observed up until 90 days following discontinuation of the study treatment (i.e. without taking subsequent therapy into account).

All reported AEs will be listed along with the date of onset, date of resolution (if AE is resolved) and investigator's assessment of severity and relationship to study drug. Frequencies and percentages of patients reporting each preferred term will be presented (i.e. multiple events per patient will not be accounted for apart from on the episode level summaries which may be produced).

Summary information (the number and percent of patients by system organ class and preferred term separated by treatment group) will be tabulated for:

- All AEs
- All AEs possibly related to study medication (as determined by the reporting investigator)
- AEs with a maximum CTCAE grade 3 or 4
- AEs of any CTCAE grade 3 or 4

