- AEs with a maximum CTCAE grade 3 or 4, possibly related to study medication (as determined by the reporting investigator) causality to be determined first, then max grade 3 or 4
- AEs with any CTCAE grade 3 or 4, possibly related to study medication (as determined by the reporting investigator) – causality to be determined first, then maximum grade 3 or 4
- AEs with outcome of death
- AEs with outcome of death possibly related to study medication (as determined by the reporting investigator)
- All SAEs
- All SAEs possibly related to study medication (as determined by the reporting investigator)
- AEs leading to discontinuation of study medication

- AEs leading to discontinuation of study medication, possibly related to study medication (as determined by the reporting investigator)
- AEs leading to hospitalization
- AEs leading to dose interruption of study medication
- Immune mediated AEs (as determined by the reporting investigator)
- Infusion reaction AEs (as determined by the reporting investigator)

An overall summary of the number and percentage of patients in each category will be presented. In addition, a truncated AE table of most common AEs and another table showing most common AEs with CTCAE grade 3 or 4 (maximum grade and any), showing all events that occur in at least 5% of patients overall will be summarized by preferred term, by decreasing frequency in the total column (the total column will not be displayed in the AE tables). This cut-off may be modified after review of the data. When applying a cut-off (i.e. x %), the raw percentage should be compared to the cut-off, no rounding should be applied first (i.e. an AE with frequency of 4.9% will not appear if a cut-off is 5%). Summary statistics showing the time to onset and the duration of the first AE may also be presented as appropriate.

Each AE event rate (per 100 patient years) will also be summarized by preferred term within each system organ class. For each preferred term, the event rate is defined as the number of patients with that AE divided by the total duration (days) summed over patients and then multiplied by 365.25 x 100 to present in terms of per 100 patient years.

Summaries of the number and percentage of patients with AEs will be provided by maximum reported CTCAE grade, system organ class, preferred term and treatment group.

Fluctuations observed in CTCAE grades during study will be listed for those AEs which are CTCAE \geq 3.

Deaths

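### The adverse event rate per 100 patient-years counts each patient once but does not stop that patient's time at first onset, so rates for common events come out too low and a true excess is diluted

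*SAP*

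**What the plan says.** SAP 4.2.13.1 plans a rate for every preferred term within system organ class: "the event rate is defined as the number of patients with that AE divided by the total duration (days) summed over patients", then "multiplied by 365.25 x 100 to present in terms of per 100 patient years". The same section confirms that patients are counted, not occurrences: "multiple events per patient will not be accounted for apart from on the episode level summaries".

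The section does not say what the duration is a duration of. Three candidates exist:

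- The reporting window for the AE tables: "AEs observed up until 90 days following discontinuation of the study treatment or until the initiation of the first subsequent anti-cancer therapy", whichever comes first.
- Total exposure in SAP 3.4.5, which ends at "the earliest of (date of last dose date of study drug where valid dose is considered + 27 days, death date or DCO" and is not linked to the AE rate.
- Study follow-up.

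Later in 4.2.13.1 the same two words, total duration, describe how long an AESI or AEPI lasted, which is a different quantity again.

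Protocol 9.5.2 describes the summary as follows: "data presentations of the rate of AEs per person-years at risk may be produced". SAP Section 6, which lists changes from the protocol, has four entries. None concerns this rate.

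**The concern.** Once a patient has had the event, that patient cannot enter the numerator again. On the plain reading of the SAP the patient still adds time to the denominator. A first-event count belongs with time to first event; total time belongs with a count of all events. The SAP pairs one numerator with the other denominator.

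A rate per 100 patient-years is tabulated so that arms observed for different lengths of time can be compared. Here the value depends on the length of observation even when the hazard is constant, and the shortfall grows with how common the event is. The common events, where readers look first for a difference, are the ones most affected.

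**Working it through.** The documents give no adverse event rate, so there is no planned figure to reproduce. The check compares the SAP formula with a time-at-risk rate under the trial's own design assumptions.

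**Inputs from the documents**
- PFS (SAP 1.3): "The true HR of 0.65 translates to a 5.4 month benefit in median PFS over 10 months on placebo". Check: 10 / 0.65 = 15.4 months, a gain of 5.4.
- Treatment length (SAP 1.2): to progression or intolerable toxicity, "or for a maximum of 24 months, whichever occurs first".
- Reporting window (SAP 4.2.13.1): 90 days after discontinuation, 90 / 30.4375 = 2.96 months.

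**Assumptions not in the documents**
- Treatment time is the smaller of exponential PFS and 24 months. Stopping for toxicity and earlier truncation by subsequent therapy are ignored.
- The AE hazard is constant over time.
- The SAP duration is read as the whole reporting window.
- Incidence is varied because none is stated.

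**Formulas**
- SAP rate = 100 × patients with the event / sum of window lengths in years.
- Time-at-risk rate = 100 × patients with the event / sum of min(first onset, end of window) in years.
- With one fixed window, the ratio of SAP rate to true rate at incidence p is p / −ln(1 − p): 0.949 at 10%, 0.841 at 30%, 0.721 at 50%.

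**Observation time.** Mean treatment time is (1 − exp(−24λ))/λ with λ = ln 2 / median. This gives 14.7 months (durvalumab) and 11.7 months (placebo). Adding 2.96 gives mean windows of 17.6 and 14.7 months, or 1.468 and 1.221 years.

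**Worked case: placebo incidence 30%**
- SAP rate on placebo: 30 / 1.221 = 24.6. Time-at-risk rate: 31.1. Shortfall: 1 − 24.6/31.1 = 21%.
- Equal hazards: durvalumab incidence is 35.0% over the longer window, so the SAP rate is 35.0 / 1.468 = 23.8. Ratio: 23.8/24.6 = 0.97.
- True hazard ratio 1.5: durvalumab incidence is 46.6%, so the SAP rate is 46.6 / 1.468 = 31.7. Ratio: 31.7/24.6 = 1.29.

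**Results** (simulation, 2,000,000 patients per arm)

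| Placebo incidence | Placebo SAP rate | Placebo time-at-risk rate | Shortfall | SAP ratio, equal hazards | SAP ratio, true hazard ratio 1.5 |
|---|---|---|---|---|---|
| 10% | 8.2 | 8.8 | 7% | 0.99 | 1.43 |
| 30% | 24.6 | 31.1 | 21% | 0.97 | 1.29 |
| 50% | 40.9 | 64.4 | 36 to 37% | 0.94 | 1.15 |

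The time-at-risk rate returns 1.00 and 1.50 in every row. At 5% incidence the shortfall is about 3%.

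**If exposure is meant instead.** With time ending 27 days after last dose as the denominator and the 90-day numerator kept, the hazard ratio of 1.5 shows as 1.26 at 30% and 1.12 at 50%. The undefined duration therefore changes the answer.

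**Early onset.** If an equal hazard acts only in the first 3 months, the durvalumab/placebo ratio is 0.83 under the SAP and 0.83 to 0.84 under time at risk (incidence 10 to 50%). If it acts only in the first 6 months, the figures are 0.84 and about 0.85 to 0.86 (incidence 10 to 45%).

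**The case against.** The strongest reply is that this is missing detail and not an error. The SAP does not say which duration it means, and its sentence could be read together with the protocol so that time at risk is intended. The protocol wording is optional and gives no formula. That much is fair: part of the defect is lack of specification. But the SAP makes the table a planned output and defines its formula, and a programmer following that text has no instruction to stop at first onset.

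A reader might go further and infer that the formula makes durvalumab look materially safer. The documents do not support that. A ratio as low as 0.87 with equal hazards can be produced (30.1 against 34.6 at a hazard of 40 per 100 patient-years), but only by assuming 1.5 against 0.75 years of exposure. The design PFS implies 14.7 against 11.7 months on treatment, about 1.25 to 1, and then the tilt is 1% to 6%. No document states exposure by arm. That durvalumab is given for longer is inferred from the assumed PFS, and toxicity also ends treatment.

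It is also right that the remedy has limits. Protocol 4.2.3, citing an earlier durvalumab trial, says that new immune-mediated events are rare after 6 months of treatment. For such events both formulas spread an early hazard over unequal follow-up, and changing the denominator barely moves the ratio.

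Finally, safety summaries are descriptive, counts and percentages are the main display, and time to onset of the first AESI and exposure are summarised separately. That limits the consequence; it does not make the formula right.

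**Conclusion.** The point holds as a minor correction. As written, the rate pairs a count of patients with time that runs on after the event, and it differs from what Protocol 9.5.2 describes without being listed in SAP Section 6. Under constant hazards and design-based treatment time, the effect is negligible for rare events. For events affecting 30% to 50% of placebo patients, rates are 21% to 37% too low, and a true hazard ratio of 1.5 appears as 1.29 to 1.15. Dilution of a real excess is the main harm; the tilt when hazards are equal is slight. These sizes depend on the constant hazard, on the assumed PFS driving treatment time, and on reading the duration as the full reporting window. No test or decision rule depends on this table.

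**What to change.** Replace the denominator in SAP 4.2.13.1 with the time from first dose to the earlier of (a) first onset of that preferred term and (b) the end of the AE reporting window, that is 90 days after last dose or the start of first subsequent anti-cancer therapy, cut at death or data cut-off. If an event rate is preferred, count all occurrences over total time in that same window and label it so. Either way, name the window so that numerator and denominator match, and align the text with Protocol 9.5.2 or record the difference in SAP Section 6. A footnote should say that, for events with early onset, rates still reflect unequal follow-up and should be read beside the percentages.

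The cost is one sentence and a small programming change. Onset dates are already collected and listed.

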#### 8.3.2 Time period and frequency for collecting AE and SAE information

AEs and SAEs will be collected from the time of the patient signing the ICF until the follow-up period is completed (90 days after the last dose of IP). If an event that starts after the defined safety follow-up period noted above is considered to be due to a late-onset toxicity to study drug, then it should be reported as an AE or SAE as applicable.

All SAEs will be recorded and reported to the Sponsor or designee within 24 hours, as indicated in Section 8.4.1. The Investigator will submit any updated SAE data to the Sponsor within 24 hours of it being available.

Investigators are not obligated to actively seek AE or SAE in former study patients. However, if the Investigator learns of any SAE, including a death, at any time after a patient's last visit and he/she considers the event to be reasonably related to the study treatment or study participation, the Investigator should notify the Sponsor.

The method of recording, evaluating, and assessing causality of AE and SAE and the procedures for completing and transmitting SAE reports are provided in Appendix B.

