#### **8.3.11** Deaths

All deaths that occur during the study treatment period, or within the protocol-defined follow-up period after the administration of the last dose of study drug, must be reported as follows:

- Death clearly resulting from disease progression should be reported to the Study Monitor/Physician at the next monitoring visit and should be documented in the eCRF in the Statement of Death page. It should not be reported as an SAE.
- Where death is not due (or not clearly due) to progression of the disease under study, the AE causing the death must be reported to the Study Monitor/Physician as an SAE within 24 hours. It should also be documented in the Statement of Death page in the eCRF. The report should contain a comment regarding the co-involvement of PD, if appropriate, and should assign main and contributory causes of death.
- Deaths with an unknown cause should always be reported as an SAE. It should also be documented in the Statement of Death page in the eCRF. A postmortem may be helpful in the assessment of the cause of death, and if performed, a copy of the postmortem results should be forwarded to AstraZeneca Patient Safety or its representative within the usual time frames.

Deaths occurring after the protocol defined safety follow-up period after the administration of the last dose of study drug should be documented in the Statement of Death page. If the death occurred as a result of an event that started after the defined safety follow-up period and the event is considered to be due to a late-onset toxicity to study drug, then it should also be reported as an SAE.

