A summary of all deaths will be provided with number and percentage of patients by treatment group in the FAS, categorized as:

- Total number of deaths (regardless of date of death)
- Death related to disease under investigation only as determined by the investigator.
- Death related to disease under investigation and an AE with outcome of death
 - AE onset prior to subsequent therapy, which includes AEs with an onset date (or pre-treatment AEs that increase in severity) on or after the date of first dose and up to and including 90 days following the last dose of study treatment, or

up to the date of initiation of the first subsequent therapy (whichever occurs first)

- AE onset after start of subsequent therapy, which includes AEs with onset date
 >90 days following the last dose of study treatment or AE start date ≥ the date of initiation of the first subsequent therapy (whichever occurs first)
- AE with outcome of death only
 - AE onset prior to subsequent therapy (as defined above)
 - AE onset after start of subsequent therapy (as defined above)
- Death after end of safety follow up period (last dose of study treatment + 90 days) and not due to AE or disease under investigation (*)
- Unknown reason for death
- Other deaths (deaths not captured in the earlier categories) e.g. death occurring after randomization but prior to receiving treatment and which is not related to disease under investigation

This summary will be produced twice; firstly, including all deaths and, secondly, including all deaths on-treatment or within 90 days of the last dose of study treatment. Hence the category marked (*) will only appear in the first summary.

Adverse events of special interest and possible interest

Preferred terms used to identify AESI and AEPI will be listed before DBL and documented in the Study Master File. Grouped summary tables of certain MedDRA preferred terms will be produced and may also show the individual preferred terms which constitute each AESI grouping. For each grouped term, the number (%) of patients experiencing any of the specified terms will be presented by maximum CTCAE grade. Time to onset of first AESI for each grouped term will also be produced. Groupings will be based on preferred terms provided by the medical team prior to DBL, and a listing of the preferred terms in each grouping will be provided.

Additional summaries of the above-mentioned grouped AE categories will include number (%) of patients who have:

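### The all-deaths table labels every fatal AE starting more than 90 days after last dose as following subsequent therapy, even when none had been given

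*SAP*

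**What the plan says.** The Deaths part of SAP 4.2.13.1 has two categories that involve a fatal AE: death related to both the disease and an AE, and death from an AE only. Each is divided into two sub-rows.

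- The 'prior to subsequent therapy' sub-row takes AEs with onset "on or after the date of first dose and up to and including 90 days following the last dose of study treatment, or" until first subsequent therapy begins, if that is earlier.
- The 'after' sub-row is introduced as "AE onset after start of subsequent therapy, which includes AEs with onset date" in a stated window. The SAP gives that window as ">90 days following the last dose of study treatment or AE start date ≥ the date of initiation of the first subsequent therapy"; the earlier of the two limits applies.

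The definitions are written out under the first category and applied to the second by cross-reference. A separate row for late deaths reads "Death after end of safety follow up period (last dose of study treatment + 90 days) and not due to AE or disease under investigation". The table is produced twice: once for all deaths, and once for deaths on treatment or within 90 days of last dose.

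Protocol 8.3.2 ends routine AE collection 90 days after last dose. A later event that is "considered to be due to a late-onset toxicity to study drug, then it should be reported as an AE or SAE as applicable". Protocol 8.3.11 applies the same rule to fatal outcomes: "If the death occurred as a result of an event that started after the defined safety follow-up period" and that event is thought to be late-onset drug toxicity, it is also reported as an SAE.

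**The concern.** The label of the 'after' sub-row states that the patient had started another therapy before the AE began. Its definition admits AEs for which that is not so. Following the plan exactly would produce a table that makes a false statement about those deaths.

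The affected window matters for safety review. Once routine collection has ended, suspected late-onset drug toxicity is one of the stated reasons for a fatal AE to enter the database. A reader of the table could take such a death to be confounded by a later treatment that the patient never received. SAP 4.2.13.1 itself justifies the cut at 90 days or subsequent therapy as a way to isolate events attributable to study treatment, which encourages that reading.

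**Working it through.** No sample size, power or alpha figure is involved, so the check is to apply the row definitions to every combination of AE onset and subsequent therapy.

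| AE onset after last dose | Subsequent therapy | Sub-row assigned | Label true? |
|---|---|---|---|
| ≤90 days | none | prior | yes |
| ≤90 days | started after AE onset | prior | yes |
| ≤90 days | started on or before AE onset | after | yes |
| >90 days | started on or before AE onset | after | yes |
| >90 days | none | after | **no** |
| >90 days | started only after AE onset | after | **no** |

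The label fails in two of the six combinations. Three further checks:

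1. **Does the 'whichever occurs first' qualifier repair it?** No. With no therapy date, the 90-day limb alone decides. If therapy starts on day 150 and the AE on day 120, the 90-day point comes first and the AE is still placed in the 'after' sub-row.
2. **Could another row hold these deaths?** No. The 'prior' sub-row closes at 90 days. The late-death row excludes deaths due to an AE. The residual row takes only deaths not captured earlier.
3. **Does another planned table show them correctly?** No. SAP 3.4.1 summarises only treatment-emergent AEs, which end at 90 days or first subsequent therapy. SAP 4.2.13.1 applies the same cut to the AE summary tables, and its optional longer-term summaries also stop at 90 days. Protocol 9.4.2.1 sends AEs beyond 90 days to a separate listing and keeps them out of the AE summaries.

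The second version of the table is not affected. An AE that starts more than 90 days after last dose cannot have caused a death within those 90 days.

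**The case against.** The strongest reply is that the sub-rows divide deaths by time of onset and assign no cause. The definition is written out in the SAP, each death still counts in its arm and in its fatal-AE category, and the investigator's relatedness assessment remains in the AE listing. All of that stands. It limits the consequence but does not make the label true.

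Three stronger readings are tempting, and the documents do not support them.

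- **That the table attributes late drug deaths to other treatment, or understates deaths caused by durvalumab.** The table shows no causality in either sub-row, and category totals by arm do not change. Nor do the documents say what share of fatal AEs beyond 90 days would be suspected drug toxicity; some will follow a real subsequent therapy and be labelled correctly.
- **That the mislabelling falls mainly on the active arms.** Under the design PFS assumptions (exponential, medians 15.4 and 10 months, 262 per arm), the numbers event-free at 24 months are 262 × exp(−ln2 × 24/15.4) = 262 × 0.340 ≈ 89 on durvalumab and 262 × exp(−ln2 × 24/10) = 262 × 0.189 ≈ 50 on placebo. These are event-free patients, not late fatal AEs. The count omits patients who stop early for toxicity. It also omits those who progress and receive no systemic therapy, or only radiotherapy, which SAP 4.2.21 does not count as subsequent therapy. More placebo patients progress or die by 24 months (262 − 50 = 212 against 262 − 89 = 173), which pulls the other way. The combination arm is not covered at all.
- **That the two sub-rows overlap on the day subsequent therapy starts.** The 'prior' definition includes day 90 explicitly but does not say the same of the therapy start date, so the natural reading is that this date is excluded. SAP 3.4 includes that date, but in its definition of on-treatment assessments. At most this is an ambiguity.

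The number of affected deaths may also be small. Protocol 4.2.3 cites earlier durvalumab data in which the probability of new immune-mediated events was very low beyond 6 months of treatment.

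**Conclusion.** The point holds as a labelling error built into a stated rule. In the all-deaths version, under both fatal-AE categories, every fatal AE with onset more than 90 days after last dose is reported as following subsequent therapy. That is false when no such therapy was given, or when it began only after the AE. These deaths can include suspected late-onset drug toxicity, and no other planned summary table shows them.

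The effect stops at the sub-row counts. Total deaths, fatal-AE category totals, the within-90-days version and every formal test are unchanged. The size cannot be computed, because the documents give neither an expected number of such deaths nor a direction between arms. The conclusion rests only on the row definitions as written. It should be corrected because it makes a main safety table state something untrue, although the practical effect may be small.

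**What to change.** Under both parent categories, keep the 'prior' sub-row and split the 'after' sub-row in two:

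- onset on or after the start of a subsequent therapy actually received;
- onset more than 90 days after last dose, with no subsequent therapy started on or before the AE onset date.

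State in the 'prior' sub-row that onset must be strictly before the start of subsequent therapy, which removes any doubt about the boundary day. Showing investigator causality for the new late-onset row would help readers but is not needed to correct the label.

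The minimum change is to rename the existing row along the lines of: AE onset >90 days after last dose or on/after start of subsequent therapy (whichever occurs first). That removes the false statement but leaves the two kinds of death mixed.

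The cost is one SAP paragraph and one table shell. All the dates are already collected.
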